4.1 Study overview

Phase II, multicenter, comparative, controlled, parallel-group, open-label, randomized clinical trial.

Justification of the study design.

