
Stage 1:
 
• Education according to the disease, its management, treatment and prognosis• Modification of the local environment• Education according to dietary modifications• Identification and modification/elimination of topical and systemic offending medications• Eye lubricants• Eyelid hygiene and warm compresses 
Stage 2: If the above options are inadequate, consider the following:
 
• Treatment for Demodex• Tear Conservation
○ Lacrimal Occlusion○ Wet Camera Goggles• Nighttime treatments (e.g. ointments)• Physical warm-up and expression of meibomian glands• Pulsed Light Therapy
○ Antibiotics or their combination with steroids on palpebral margins○ Topical steroids (limited duration)○ Topical immunomodulators○ Topical LFA-1 antagonists○ Topical macrolides or tetracyclines 
Stage 3:
 
• Oral secretagogues• Autologous serum• Therapeutic contact lenses 
Stage 4:
 
• Topical steroids (extended duration)• Amniotic membrane grafts• Surgical occlusion of puncta.• Other surgical approaches.

Table 2. Stages of Dry Eye Treatment

Treatment algorithms are often built to recommend a sequence of treatments according to the stage of the disease, but this is not possible for dry eye, as it is a complex condition that varies from patient to patient in both severity and in character. However, with the intention of helping ophthalmologists to create a logical and evidence-based treatment approach, the treatment algorithm shown in Table 2 was proposed within the framework of the TFOS DEWS II. For patients who do not respond to a certain level,

or who show greater severity, the next level is recommended, and in some cases, previous treatment may continue, in addition to any new treatment. In general, the approach is to start with conventional low-risk and normally available treatments, such as eye lubricants for the early stages of the disease, and progress to more advanced treatments for more severe clinical conditions.

The characteristics of the tear film and the hydrodynamics of the lacrimal system mean that ophthalmic formulations have a short retention period on the ocular surface, which is why frequent application is necessary to achieve the appropriate concentration of the substance used. [19]

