3.4 Hypotheses

H₀: Multi-dose Lagricel® Ofteno decreases the OSDI test score by 20% or more at the end of the study in at least 1 of the proposed dosages.

H₁: Multi-dose Lagricel® Ofteno does not decrease the OSDI test score by 20% at the end of the study in at least 1 of the proposed dosages.

4. Study design

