4.2 Justification of the study design

The design of the study (clinical trial) is considered the highest standard of data quality when seeking to explore the effect of an intervention. The drug development phase (phase II) corresponds to the objective of the study, which is to evaluate efficacy and ideal dosage. The presence of parallel groups allows comparison between intervention groups on outcome variables. Due to the nature of the design, blinding was not considered for this study.

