5.3 Lifestyle considerations

For the study, participants may need to modify some lifestyle activities to comply with the following:

- Abstain from tobacco use.

- Refrain from using electronic vaporizers.
- Avoid submerging yourself in water without eye protection (*goggles*).
- Avoid direct exposure to fans (including air conditioning vents) during activities that involve vision. 24 hours before your check-up visits.
- Maintain your sleep-wake cycle with which you enter the study.

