6.1 Administered product

1. Investigational product

- Generic name: Sodium hyaluronate.
- Distinctive name: Multi-doses Lagricel® Ofteno.
- Active ingredients: Sodium hyaluronate 0.4%.

- 
- Pharmaceutical form: Ophthalmic solution.
 - Presentation: Multi-dose dropper bottle.
 - Prepared by: Laboratorios Sophia, S.A. de C.V.
 - Solution Description: Transparent solution, free of visible particles.
 - Packaging description: White bottle with a capacity of 10 mL, made of low-density polyethylene.

2. Dose of the investigational medicinal product

Three different dosages will be used, each of the groups will use one of the following:

- One drop BID, OU, for 30 days (suggested time between applications is 12 hours).
- One drop QID, OU, for 30 days (minimum time between applications of 3 hours).
- One drop 6x/D, OU, for 30 days (minimum time between applications of 3 hours).

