10.2.2 Justification of the sample size calculation

The sample size calculation was made based on the study by Pinto-Fraga et al. (2017), where they evaluated the safety and efficacy of an artificial tear of 0.2% hyaluronic acid (HA) versus SS (saline, 0.9% NaCl) in patients with mild dry eye (OSD) after one month of treatment. Subjects treated with HA had a decrease of -19.66% with respect to their initial mean value, while in subjects treated with SS there was a significant increase in the final OSDI score of 12.47%, $p < 0.05$ compared to the initial [61].

For the calculation, a decrease in the OSDI score of 20% was considered for the formulation proposed in this protocol (Multi-dose Lagricel® Ofteno) with respect to its initial mean value in subjects with mild to moderate DED.

The sample size was calculated using the equation for two proportions [62], considering a power of 80% (β), a significance level of 0.05 (α) and a non-inferiority margin (δ) of 10%, based on the following working hypotheses:

$$H_0: P_A - P_B \leq \delta$$

$$H_1: P_A - P_B > \delta$$

Where, δ is the margin of non-inferiority and the ratio between the sample size of the two groups is:

$$k = \frac{n_A}{n_B}$$

The calculation to estimate the sample size and power was done using an online tool and following the equations [63]:

$$n_A = kn_B, n_B = \left(\frac{P_A(1 - P_A)}{k} + P_B(1 - P_B) \right) \left(\frac{z_{1-\alpha} + z_{B-\beta}}{P_A - P_B - \delta} \right)^2$$
$$1 - \beta = \Phi(z - z_{1-\alpha}) + \phi(-z - z_{1-\alpha}), z = \frac{P_A - P_B - \delta}{\sqrt{\frac{P_A(1 - P_A)}{n_A} + \frac{P_B(1 - P_B)}{n_B}}}$$

Where:

- $(k = \frac{n_A}{n_B})$ is the allocation ratio,
- (Φ) is the standard normal distribution function,
- (α) is the Type I error,
- (β) is the Type II error, meaning that $(1 - \beta)$ is the power, and
- (δ) is the test margin.

According to the previous calculation, the result is 39 subjects, this calculation was increased by 20% considering possible losses (8 subjects). The total suggested sample size is 141 subjects (47 subjects per treatment dosage), who will contribute OU to the study.

11. Ethical considerations

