16.1 OSDI

Identification card	
No. of Study: SOPH037-1219/II	Date:   /   /  
Subject's initials:  	Subject No.: 037-   -  

Directions:

The OSDI test is a simple test created to establish a severity/classification of dry eye according to its symptoms. Answer the following questions by checking the box that best represents your answer:

Over the past week, Have you experienced any of the following alterations?	Frequency				
	In every moment	In almost every moment	50% of the time	Almost in no moment	In no moment
1. Light sensitivity	4	3	2	1	0
2. Gritty feeling in the eyes	4	3	2	1	0
3. Eye pain	4	3	2	1	0
4. Blurred vision	4	3	2	1	0
5. Poor vision	4	3	2	1	0
Subtotal of the answered cells					(A)

[figure not shown]
[figure not shown]
[figure not shown]
Over the past week, Have you had eye problems that have limited you to perform these actions?	Frequency					NA
	In every moment	In almost every moment	50% of the time	Almost in no moment	In no moment	
6. Read	4	3	2	1	0	NA
7. Driving at night	4	3	2	1	0	NA
8. Working with a computer or an ATM	4	3	2	1	0	NA
9. Watch TV	4	3	2	1	0	NA
Subtotal of the answered cells					(B)	

Over the past week, Have you felt discomfort in eyes with any of the following situations?	Frequency					NA
	In every moment	In almost every moment	50% of the time	Almost in no moment	In no moment	
10. Wind	4	3	2	1	0	NA
11. Places with low humidity (dry)	4	3	2	1	0	NA
12. Air-conditioned areas	4	3	2	1	0	NA
Subtotal of the answered cells					(C)	

Sum of A+B+C = (D)

Number of items answered, do not include responses as N (E)

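### A 20% OSDI fall from each dosage's own baseline cannot establish product efficacy, because every arm receives the product

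*Combined protocol and SAP*

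**What the plan says.** The synopsis and section 4.1 call the trial a "Phase II, multicenter, comparative, controlled, parallel-group, open-label, randomized clinical trial". Section 6.1 sets out the arms: "Three different dosages will be used, each of the groups will use one of the following", followed by one drop twice, four times or six times daily of the same product. There is no vehicle, saline, other-lubricant or untreated arm. Section 4.2 explains the grouping: "The presence of parallel groups allows comparison between intervention groups on outcome variables".

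The main objective (3.1) is efficacy judged by improvement in OSDI. The hypothesis in 3.4 is that the product "decreases the OSDI test score by 20% or more at the end of the study" in one or more dosages. Section 10.2.2 makes clear that the 20% is relative to the group's own starting mean, and 10.1.2 plans within-group tests alongside post-hoc comparisons between groups.

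The 20% is taken from a study of 0.2% hyaluronic acid against saline. Its active arm changed by -19.66%, "while in subjects treated with SS there was a significant increase in the final OSDI score of 12.47" per cent.

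Section 5.3 lists lifestyle conditions, including tobacco, vaporizers and this one: "Avoid direct exposure to fans (including air conditioning vents) during activities that involve vision. 24 hours before your check-up visits". The treatment-stages table in the Framework section lists "Modification of the local environment" under Stage 1. The questionnaire in 16.1 has a one-week recall and includes item "12. Air-conditioned areas". OSDI is taken only at the basal and final visits (1.3 and Table 3).

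**The concern.** The success criterion is a before-and-after change within each arm, and nothing in the design says what that change would have been without the product. Subjects know they are on active drops, and they score their own symptoms. They were selected on the same score, they are followed for a month, and they may have changed habits for the study. Each of these can move OSDI.

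The Framework section says the sponsor wants to demonstrate efficacy in this trial, and 2.4.2 promises both to document efficacy and to establish the ideal dosage. The randomized arms can inform the second aim. The 20% criterion is offered for the first, and meeting it would not show that the product caused the fall.

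**Working it through.** **1. The plan's own sample-size figure.** 39 × 1.2 = 46.8, rounded to 47 per group; 47 × 3 = 141. This step reproduces. The 39 comes from a two-proportion formula in P_A, P_B and a 10% margin. One set of inputs that returns it is P_A = 0.20, P_B = 0.10, δ = -0.10, one-sided 0.05, power 80%: (0.16 + 0.09) × [(1.645 + 0.842)/0.20]² = 38.64. The plan does not state P_B = 0.10 and does not say which arm is A or B. No expected difference between dosages is given, so 47 per group was not derived for a dosage contrast.

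**2. What the source study compared.** Between arms: -19.66 - 12.47 = -32.13 percentage points. Within the active arm: -19.66%. The plan carries over only the within-arm figure. The two differ because the saline arm did not stay at zero.

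**3. How often the criterion is met with no product effect.** The documents give neither an SD nor a background change, so both are assumed: mean background fall b (%), SD of percentage change 30 to 50, n = 47 per arm, normal arm means, independent arms.

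P(at least one of three arm means falls 20% or more) = 1 - [1 - Φ((b - 20)/(SD/√47))]³

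Example, b = 15 and SD = 30: SE = 30/√47 = 4.38; z = -5/4.38 = -1.14; Φ = 0.127; 1 - 0.873³ = 0.33.

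| Background fall b | Probability, SD 30 to 50 |
|---|---|
| 0% | under 1% |
| 10% | 3% to 23% |
| 15% | 33% to 57% |
| 20% | 88% |

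If the background were instead a 12.47% rise, as on saline in the cited study, then at SD = 50 z = (-12.47 - 20)/7.29 = -4.45, and the probability is negligible.

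For the planned within-group test against no change (two-sided 0.05), the chance per arm is Φ(b/(SD/√47) - 1.96). At b = 10 this gives 0.63 (SD 30) to 0.28 (SD 50), so at least one significant arm occurs with probability 95% to 62%.

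**4. How sensitive one subject's score is.** Section 7.4.5.1 gives OSDI = 25D/E. With all 12 items answered, one step on one item is 25/12 = 2.08 points. A 20% fall is 2.6 points (1.25 steps) at baseline 13 and 6.4 points (3.07 steps) at baseline 32. One step on each of two items is 4.17 points: 32% at baseline 13, 20% at 20.8, 13% at 32.

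A change to NA can act either way. Start from a sum of 10 over 12 items (20.83):

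- An item scored 3 becomes NA: 7 × 25/11 = 15.91 (-23.6%).
- An item scored 1 becomes NA: 9 × 25/11 = 20.45 (-1.8%).
- An item scored 0 becomes NA: 10 × 25/11 = 22.73 (+9.1%).

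These figures describe the scale. They do not estimate bias in a group mean.

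**5. Timing of the lifestyle conditions.** Section 5.3 gives no start date. Consent must precede any procedure (11.4.1), consent and baseline OSDI fall at the basal visit (1.3, 7.4.6.2), and dosing begins on D1 (6.3). No run-in is described, although 5.2.1 sets a 15-day pre-inclusion condition for contact lenses. That the changes begin at about the same time as the drops is therefore an inference. If the 24-hour phrase limits the fan rule, it covers about one of the seven recall days before the final visit. The text does not say whether the basal visit counts as a check-up visit.

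**The case against.** The strongest reply is that the trial is controlled: randomized concurrent dosage groups are a control for choosing a dosage, which is the purpose given in 4.2. That stands. A reader might infer that the label is simply wrong, but the documents support it as a dosage comparison. They do not support extending it to the 20% criterion.

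A second tempting reading is that the lifestyle rules could produce the 20% fall by themselves. The text does not carry that. The fan rule concerns direct exposure during visual tasks, not air-conditioned areas in general, and may last only 24 hours. Nothing in 5.3 addresses outdoor wind or dry places. Subjects who do not smoke or vape have nothing to change there, and one rule asks them to keep their existing sleep pattern. The size of any effect is unknown.

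A third reading is that background change must favour the product. The only figure in the documents for change without hyaluronate points the other way, and selection within a range bounded at both ends can shift a mean in either direction. That leaves the direction uncertain; it does not supply the missing comparison.

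It is also fair to say that between-group ANOVA with post-hoc tests is already planned, so the better analysis needs no inventing. It has its own limits: subjects know whether they use two or six drops a day, so expectation may differ by arm.

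**Conclusion.** The point holds in this form: a fall of 20% or more from a dosage's own baseline, in an open-label trial where every arm receives the product, does not establish product efficacy. This follows from the design and does not depend on the lifestyle rules, which are only a possible further contributor.

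The consequence cannot be sized from the documents. Under the assumed SDs and no product effect, the criterion would almost never be met with a flat or rising background, would be met about a third to over half of the time with a 15% background fall, and in 88% of trials with a 20% fall. Which case applies is what a concurrent arm without the product would have shown. Between-dosage contrasts keep the protection of randomization, subject to expectation differing by frequency.

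**What to change.** 1. In 3.1, 3.4, 4.1 and 10.1.2, state that there is no untreated or vehicle control and that the concurrent comparators are the other dosages.
2. Rest the inferential conclusion on the between-dosage OSDI contrasts already planned. Report within-dosage change and the 20% criterion descriptively, not as evidence of product efficacy.
3. State that 47 per group was not derived for a dosage contrast, and that open-label expectation may differ by drop frequency.
4. Add a sensitivity OSDI computed only from items answered at both visits.
5. Reconcile 5.3 with the visit schedule in 1.3 and 7.4.6.2, so that it is clear when the lifestyle conditions begin and whether the same conditions apply before the baseline and follow-up measurements.

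The cost is wording and one extra analysis, with no added arm, subject or visit. Item responses are on the questionnaire, but 7.4.5.1 mentions only the score going into the eCRF, so item-level capture should be confirmed. The real price is a narrower claim: no dosage could be declared efficacious from its own baseline change, and the precision of the dosage contrasts would be whatever 47 per group happens to give.

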4.2 Justification of the study design

The design of the study (clinical trial) is considered the highest standard of data quality when seeking to explore the effect of an intervention. The drug development phase (phase II) corresponds to the objective of the study, which is to evaluate efficacy and ideal dosage. The presence of parallel groups allows comparison between intervention groups on outcome variables. Due to the nature of the design, blinding was not considered for this study.

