7.4 Outcome variables

7.4.1 Primary outcome of efficacy

- OSDI test score (ET: day 31).

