7.4.5.1 OSDI Score

The OSDI is a validated and reliable instrument to measure the severity of dry eye, it has the necessary psychometric properties to be used as an outcome variable in clinical studies. [49] It consists of a questionnaire with 3 questions and 12 items, the answer is in frequency and offers 5 options from 4 (at all times) to 0 (at no time), questions 2 and 3 also contain the NA option. (See: 16.1) The OSDI score is calculated based on the following formula:

$$\text{OSDI} = \frac{D \times 25}{E}$$

Where:

D = sum of the points of the questions answered

E = number of items answered, those answered with NA are not counted as answered

The OSDI score will be recorded on the electronic Case Report Form (eCRF).

Management as AE: An increase of more than 40% in the value of the OSDI score at the basal visit should be reported and managed as an AE for lack of effectiveness.

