7.4.6 Study visits and activity programs

7.4.6.1 Description of activities per visit

The procedures are listed in the order in which they are suggested, trying to maintain the coherence of the evaluations and as far as possible, from the least invasive to the most invasive

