7.4.6.2 Basal Visit

- Signature of the CRF: refers to the signing of the written informed consent document. Without obtaining informed consent, it is not possible to perform any of the study procedures
- Clinical history: refers to the technical, clinical, and legal document in which the subject's health conditions, medical acts, and other procedures performed on the subject are chronologically recorded. It includes anthropometric measurements, anamnesis, comprehensive ophthalmological examination that allows discerning the patient's eligibility, that is, evaluation of both eyes of ocular adnexa, slit lamp examination of the ocular surface and anterior segment and funduscopy. If the subject is taken from the established population base of the study center, the existing medical history may be used, and only an update must be made.
- Evaluation of concomitant medications: refers to the interrogation by the PI of the subject, inquiring about the use of medications.
- Urine pregnancy test: This refers to performing a rapid pregnancy test on all women of childbearing potential who wish to enter the study. By fertile age we mean women who have had their menarche and have not presented their menopause. Menopause is defined as 12 months from the last menstruation in women over 40 years of age, or who have had a hysterectomy or bilateral oophorectomy. Women of childbearing potential with contraceptive methods including bilateral tubal obstruction should be tested for pregnancy. This test will be performed by the PI or designated team person in accordance with the instructions on the device provided by the sponsor
- Vital signs: refers to the measurement of heart rate, respiratory rate, systemic blood pressure and temperature. This information must be contained in the patient's medical history and the evolution notes of the patient's clinical file.

- BCVA: See 7.4.5.8
- OSDI: See 7.4.5.1
- TFRT: See 7.4.5.2
- Ocular Surface Staining See 7.4.5.3 and 7.4.5.4
- Ophthalmologic evaluation: refers to the evaluation of the subject's ophthalmic structures, eyelids and adnexa, ocular surface, anterior segment, and posterior segment; not considered within the outcome variables. This evaluation is intended to identify alterations that may interfere with the course of the investigation or identify AEs. This examination will be recorded in the clinical file, in the CRF only what is considered an AE will be reported.
- IOP: See 7.4.5.9

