7.4.6.4 Final visit

- Concomitant Drug Evaluation: See 7.4.6.2
- Urine Pregnancy Test: See 7.4.6.2
- Vital Signs: See 7.4.6.2
- BCVA: See 7.4.5.8
- Tear Film Rupture Time: See 7.4.5.2
- Ocular Surface Staining: See 7.4.5.3 and 7.4.5.4
- Comprehensive ophthalmologic evaluation: See 7.4.6.2
- IOP: See 7.4.5.9
- AE Evaluation: Ver 7.4.5.7
- OSDI: See 7.4.6.2

- Evaluation of the subject's diary: Refers to the review of the subject's diary instrument by the PI or the staff of the designated center; it will be reviewed that it is correctly filled in, as well as the patient's comments, of these comments the PI may interrogate for AEs. At the discretion of the PI, comments may or may not be reported as AEs.
- Evaluation of adherence: See 7.4.6.4
- Return of IP and subject's diary: refers to the subject's return of the IP and the subject's diary to the research center.

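### The patient-reported primary outcome (OSDI) is listed before the dye tests, tonometry and AE questioning at the basal visit but after them at the final visit, which may bias the within-group change

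*Combined protocol and SAP*

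**What the plan says.** Section 4.1 describes the trial as "Phase II, multicenter, comparative, controlled, parallel-group, open-label, randomized clinical trial", and section 4.2 adds "Due to the nature of the design, blinding was not considered for this study". All three arms receive the same product at different frequencies; there is no vehicle or untreated arm.

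Section 7.4.1 gives the primary efficacy outcome as "OSDI test score (ET: day 31". Section 7.4.5.1 describes the instrument: "It consists of a questionnaire with 3 questions and 12 items". The form in Annex 16.1 is addressed to the subject, and its questions begin "Over the past week". The hypothesis in section 3.4 is a reduction of at least 20% in one or more dosages. Table 3 (7.4.5) schedules the OSDI at the basal and final visits and assigns ANOVA, with Student's t-test where applicable.

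On sequence, section 7.4.6.1 states: "The procedures are listed in the order in which they are suggested". It adds that gentler procedures should come ahead of more invasive ones as far as possible. The basal list (7.4.6.2) has the entry "OSDI: See 7.4.5.1" straight after BCVA. The final list (7.4.6.4) has "OSDI: See 7.4.6.2" straight after AE evaluation. Section 7.4.5.1 does not say at what point in a visit the questionnaire is to be completed.

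**The concern.** A within-group change is interpretable only if the two scores are taken under the same conditions. As listed, the basal score comes before the dye tests, tonometry and AE questioning, and the final score comes after them. By then the subject has had topical anaesthetic and fluorescein (7.4.5.3), lissamine green (7.4.5.4), tonometry (7.4.5.9) and directed questioning about AEs (7.4.5.7). The AEs expected under 7.4.5.7 include irritation, foreign body sensation and blurred vision. These overlap with OSDI items on grittiness, pain and blurred vision.

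Subjects know their dosing frequency, and no vehicle arm shows what change occurs without active treatment. Any effect of questionnaire position would therefore be counted as part of the treatment effect when the 20% criterion is applied.

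**Working it through.** **1. The two lists side by side (7.4.6.2 and 7.4.6.4)**

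| Procedure | Basal visit | Final visit |
|---|---|---|
| Clinical history, with slit lamp and funduscopy | before OSDI | not listed |
| BCVA | before OSDI | before OSDI |
| TFRT (fluorescein) | after OSDI | before OSDI |
| Staining (anaesthetic, dyes) | after OSDI | before OSDI |
| Ophthalmologic evaluation | after OSDI | before OSDI |
| IOP | after OSDI | before OSDI |
| AE evaluation | after OSDI | before OSDI |
| Diary review | not applicable | after OSDI |

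Five procedures change sides. The final-visit order also sits badly with two of the plan's own provisions. A questionnaire listed after drops and tonometry departs from the gentle-first principle in 7.4.6.1. And 7.4.5.1 makes an OSDI rise of more than 40% over the basal value a reportable AE, yet AE evaluation is listed before the score that would reveal it.

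**2. Which comparison is exposed**

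Let B be an arm's mean basal score, F its mean final score without a position effect, and s the mean shift caused by the later position.

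- Within an arm, the observed fractional fall is (B − F − s)/B, which is the true fall minus s/B. The shift stays in.
- Between arms j and k at day 31, (Fj + s) − (Fk + s) = Fj − Fk. A shift common to the arms cancels.

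**3. Scale**

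The plan gives no figure for s, so there is none to reproduce, and the sample size (39 per group, raised to 47) does not enter. What can be calculated is the coarseness of the instrument. From 7.4.5.1, OSDI = 25 × D/E. With all 12 items answered, one response step on one item is 25/12 = 2.08 points. The entry range is 13 to 32 (5.1.1), with midpoint (13 + 32)/2 = 22.5.

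| Baseline | 20% fall (points) | Steps needed (20% fall ÷ 2.08) | One step as % of baseline | One step as % of the 20% fall |
|---|---|---|---|---|
| 13 | 0.20 × 13 = 2.6 | 1.2 | 16.0% | 80% |
| 22.5 | 0.20 × 22.5 = 4.5 | 2.2 | 9.3% | 46% |
| 32 | 0.20 × 32 = 6.4 | 3.1 | 6.5% | 33% |

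As an illustration, suppose the arm mean at baseline is 22.5, the true fall is 20%, and the average shift is one step. The observed fall would be 20 + 9.3 = 29.3% if the shift lowers final scores, or 20 − 9.3 = 10.7% if it raises them.

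The shift has to be an average over the arm. One step in one subject moves a mean of 47 by only 2.08/47 = 0.04 points.

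**The case against.** The case on the other side is substantial, and most of it limits the point rather than removing it.

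- **The order is only suggested.** True, so sites may do otherwise. But then nothing fixes when the primary outcome is taken, and the only guidance given differs between visits.
- **An eye examination already precedes the basal OSDI.** True: the clinical history, listed second, includes slit lamp and funduscopy. A reader might infer that the basal score is taken before any examination; the text does not support that. The asymmetry is confined to the five procedures tabulated.
- **The recall period is the past week.** An anaesthetic given minutes earlier cannot alter last week's symptoms. This limits an immediate effect but does not exclude an influence on how symptoms are recalled and rated after an examination and symptom questioning.
- **The primary outcome is defined as the day 31 score, not a change.** True of 7.4.1. The hypothesis is nevertheless a fall from the initial value, so the within-group reading is in use.
- **The schedule in section 1.3 lists the OSDI below the examination and AE rows for both visits.** Those rows cannot be chronological: the OSDI row also falls below eligibility and product assignment, yet the score is an entry criterion. The schedule neither confirms nor cures the difference.

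A reader might also infer that investigators discuss findings with subjects before the questionnaire. The documents describe directed questioning and recording, not disclosure of findings.

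**Conclusion.** The listed position of the OSDI differs between the two visits on which the 20% criterion depends, and no reason is given. This creates an avoidable risk of bias in the within-group change.

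Three stronger readings are not supported:

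- That the change score **is** biased. The documents give neither direction nor size, and the later position could raise or lower reported symptoms.
- That the dose comparison is biased by the order. The list is the same in all arms, so a common shift cancels. This rests on the shift not depending on dosing frequency. Subjects' knowledge of their frequency is a separate limitation of an openly declared open-label design.
- That one to three item steps measure the bias. They show how small an average shift would be material (one step is 33% to 80% of the target fall, assuming all 12 items are answered), not that such a shift occurs.

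The point is modest in weight, but it concerns the primary measurement and is easy to remove.

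**What to change.** In 7.4.6.2 and 7.4.6.4, list the OSDI at the same early position. The subject completes it unaided right after signing consent at the basal visit, and on arrival at the final visit. In both cases it comes before any eye examination (including the one within the clinical history), any drops and any AE questioning. State in 7.4.6.1 or 7.4.5.1 that this position is required, while the rest of the order remains suggested.

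The cost is one line moved in each list and one added sentence, plus the usual amendment review under section 11.2 if the protocol is already approved. No staff, visits, procedures or subjects are added, and no sample-size figure changes. At the final visit, the OSDI result is then available when AEs are evaluated, as the 40% rule in 7.4.5.1 needs. The change does not address subjects' knowledge of their dosing frequency.
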